9.4 Secondary Analysis Methods

Unless otherwise specified, changes from baseline in continuous secondary outcomes will be compared between treatment groups using an MMRM model as specified for the primary outcome and analogous generalized linear models will be used for any repeated dichotomous outcomes.

A Hochberg multiple comparison adjustment will be applied to the 5 key secondary endpoints to maintain the overall Type 1 error rate. Treatment groups will be compared for the secondary endpoints as described in Section 7.7.

Treatment groups will be compared for the total amount of packed red blood cell transfusions (units) and iron (mg) infused during the 24-week treatment period (calculated as average over a 4-week period), using an analysis of covariance or rank analysis of covariance if not normally distributed, with adjustment for the measure in the 6 months prior to the screening period and pooled clinical site. If packed red blood cell transfusions are rare, then we will switch to a zero-inflated Poisson regression model or logistic regression, depending on the distribution.

Blinded data review prior to database lock determined the number of RBC transfusions is rare and so RBC transfusions during the 24-week treatment period will be analyzed as yes/no using logistic regression with adjustment for transfusion in the 6 months prior to screening (yes/no) and pooled site.

The blinded data review also indicated the amount of iron infused during the 24-week treatment period is not normally distributed and will be analyzed with rank analysis of covariance (Stokes, Davis and Koch 2000). The rank ANCOVA is completed in 3 steps, (A) ranking the outcome variable and the baseline value separately within each pooled site, (B) obtaining the residuals from a regression of the ranked outcome variable on the ranked baseline variable, separately for each pooled site, and then (C) comparing the treatment groups for the residuals using a Mantel-Haenszel mean score test stratified by pooled site.

Sample SAS code for the rank ANCOVA is as follows:

```
proc rank nplus1 ties=mean out=ranks;
  by sitenum;
  var [outcome variable] [baseline variable]
run;

proc reg data=ranks;
  by sitenum;
  model [outcome ranked variable] = [baseline ranked variable];
  output out=redidual r=resid;
run;

proc freq data=redidual noprint;
  tables sitenum*trtgp*resid / cmh ;
run;
```

Groups will be compared for the proportion of patients relapsed, requiring no blood or iron, and requiring endoscopic interventions and other yes/no categorical outcomes using logistic regression with adjustment for baseline assessment (ESS score, whether the patient had required a blood transfusion or required an total iron infusion amount of at least 250 mg in the 6 months before the baseline visit, and ESS score, respectively), and study site. If events are rare, exact logistic regression will be used.

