Patients will be seen every four weeks during the study to measure the ESS (with 4 week recall), measure iron stores, and obtain laboratory studies, which will include CBC, metabolic profile and iron studies. The iron replete state will be defined as a ferritin  $\geq$  50 ng/ml and a transferrin saturation  $\geq$  30% (since ferritin levels may be elevated due to concurrent inflammation). Investigators will be encouraged to replete iron stores in patients in both arms of the study based on these parameters, and the amount of iron infused (in mg) recorded. There is no mandate for the use of a particular iron preparation. Investigators will be encouraged to use iron infusions prior to blood transfusion, though the latter will be mandated for a hemoglobin below 6.5 gm/dl, and recorded as units of packed red blood cells administered. Blood transfusion may also be given at the investigator's discretion based on symptoms that may include shortness of breath, severe fatigue, or other cardiovascular manifestations. Patients will be assessed for adverse events (AE) throughout the study. Treatment dosage may be reduced, or temporarily or permanently discontinued following AE-specific guidelines related to fatigue, cytopenias or other toxicities.

The effect of pomalidomide on QOL will be assessed by measuring QOL at the baseline visit, at the 12 and 24 week visits, and at the 4 week post-treatment follow-up visit using validated NIH instruments of 1) Neuro-QOL satisfaction with social roles and activities, 2) PROMIS emotional distress – depression, and 3) PROMIS fatigue. We will also assess responses to an HHT specific questionnaire developed specifically for this study and shown to correlate with these PROMIS items. The effect of pomalidomide on duration of epistaxis will be assessed via diary between weeks 8-12, 20-24 and the 4 weeks post-treatment discontinuation.

---

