## 5 STUDY ENROLLMENT AND WITHDRAWAL

### 5.1 PARTICIPANT INCLUSION CRITERIA

1. A clinical diagnosis of HHT as defined by the Curacao criteria
2. Age  $\geq$  18 years
3. Platelet count  $\geq 100 \times 10^9/L$
4. WBC  $\geq 2.5 \times 10^9/L$
5. INR  $\leq 1.4$  and normal  $\pm 2$  sec activated partial thromboplastin time (aPTT or PTT per local laboratory designation) by local laboratory criteria (except for patients on a stable dose of warfarin or direct oral anticoagulants)
6. Epistaxis severity score  $\geq 3$  measured over the preceding three months, measured at the screening visit
7. A requirement for anemia, as determined by local laboratory hemoglobin assessment and normal ranges, and/or parenteral infusion of at least 250 mg of iron or transfusion of 1 unit of blood over the 24 weeks preceding the screening visit
8. All study participants must agree to be registered into the FDA mandated POMALYST REMS® program, and be willing and able to comply with the requirements of the POMALYST REMS® program
9. Females of childbearing potential (FCBP)† must adhere to the pregnancy testing schedule mandated by the POMALYST REMS® program (see Section 8.4.5)
10. Ability to understand and sign informed consent

†A female of childbearing potential is a sexually mature woman who: 1) has not undergone a hysterectomy or bilateral oophorectomy; or 2) has not been naturally postmenopausal for at least 24 consecutive months (i.e., has had menses at any time in the preceding 24 consecutive months).

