### 7.3 STUDY SCHEDULE

#### 7.3.1 SCREENING

Each patient will require a screening visit to determine study eligibility. During the screening period the following information will be obtained.

- Informed consent of potential participant verified by signature on written informed consent
- Review enrollment criteria
- Review medical history
- Review of medication history
- Complete ESS with 3-month recall
- Documentation of packed red blood cell transfusions and/or iron infusions over the previous six months
- Performance of a detailed physical exam

- Collect blood for CBC, ferritin, iron and TIBC, renal and liver function, INR and aPTT (or PTT per local laboratory designation), and pregnancy testing for women of child bearing potential.
- Collect biorepository blood samples (if visit is in-person)
- Determine need for parenteral iron therapy based on results of iron studies.
- Provide participants with instructions for recording epistaxis duration between screening and enrollment/baseline visit.
- Schedule study visits for eligible patients.
- Provide participants with instructions for attending the baseline visit.

At the site PI's discretion, the screening visit may be conducted remotely. Obtaining signed informed consent prior to collecting any information for the study is mandatory for a remote screening visit as well. Physical examination may be limited to the extent possible at a remote visit; vital signs and biorepository sample collection will be skipped for remote screening visit. Screening laboratory studies may be obtained within 2 weeks before and after the screening visit.

Participants who do not initially meet eligibility criteria, but may meet criteria at a later time may be rescreened. Screening study procedures should be repeated per protocol and Manual of Procedures for rescreening. Baseline visit (if participant meets eligibility criteria) should be scheduled based on the rescreen date.

---

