#### 10.4.3 ANALYSIS OF THE SECONDARY ENDPOINT(S)

A Hochberg multiple comparison adjustment will be applied to the 5 key secondary endpoints to maintain the overall Type 1 error rate, as described in Section 10.4.9. Treatment groups will be compared for the secondary endpoints as follows:

Treatment groups will be compared for the total amount of packed red blood cell transfusions (average units/4-week interval) and iron (average mg/4-week interval) infused during the 24 week treatment period, using an analysis of covariance or rank analysis of covariance if not normally distributed, with adjustment for baseline value, defined as the average amount over the 6 months prior to the screening visit and clinical site. Missing data from early discontinuations will be addressed assuming MAR by averaging each subject's available data. Sensitivity analyses will be specified in the SAP. If packed red blood cell transfusions are rare, then we will switch to either a zero-inflated Poisson regression model or logistic regression.

Groups will be compared for the proportion of patients relapsed, requiring no blood or iron, and requiring endoscopic interventions using logistic regression with adjustment for baseline assessment (ESS score, whether the patient had required a blood transfusion or required an iron infusion of at least 250 mg in the 6 months before the screening visit, and ESS score, respectively), and study site.

Treatment group comparisons of the ESS score averaged over the week 16, 20, and 24 week visit assessments and at each study visit will be assessed in the same model as the primary outcome.

Change from baseline in weekly epistaxis duration averaged over weeks 8-12, 20-24, and 4 weeks after treatment, and Quality of Life scores at weeks 12, 24, and 4 weeks after treatment will be analyzed using the same MMRM model as the ESS score.

---

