3.2.2 Key Secondary Outcomes

1. Amount of parenteral iron administered (in mg) during the 24-week treatment period in the pomalidomide and placebo groups (calculated as average mg/4-week interval to account for patients who discontinue early).
2. Amount of packed red blood cell transfusions (in units) during the 24-week treatment period in the pomalidomide and placebo groups (calculated as average units/4-week interval to account for patients who discontinue early).
3. Change in Neuro-QoL™ Satisfaction with Social Roles and Activities Short Form (V1.1) T-score from baseline (randomization visit) to weeks 12 and 24 (key timepoint), and the 4-week post-treatment follow-up visit in the pomalidomide and placebo groups.
4. Change in the HHT-specific QOL total score from baseline to weeks 12 and 24 (key timepoint), and the 4-week post-treatment follow-up visit in the pomalidomide and placebo groups.
5. Change in average daily epistaxis duration from the four-week screening period prior to baseline to weeks 8-12 and to weeks 20-24 (key timepoint), and to weeks 1-4 post-treatment in the pomalidomide and placebo groups.

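### The iron-amount key secondary endpoint is not adjusted for baseline iron status, which is collected and prognostic; this costs precision but does not bias the test

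*SAP*

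**What the plan says.** SAP 3.2.2 defines the endpoint as "Amount of parenteral iron administered (in mg) during the 24-week treatment period in the pomalidomide and placebo groups", expressed per 4 weeks. Nothing separates iron that fills a deficit present at entry from iron that replaces loss on treatment.

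Protocol 4.1 sets the target that drives infusion: "The iron replete state will be defined as a ferritin" of at least 50 ng/ml together with a transferrin saturation of at least 30%. It adds: "Investigators will be encouraged to replete iron stores in patients in both arms of the study based on these parameters". Protocol 5.1 lets patients in on "A requirement for anemia, as determined by local laboratory hemoglobin assessment and normal ranges, and/or parenteral infusion of at least 250 mg of iron" or a transfusion, so anemia with no earlier infusion is enough.

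Protocol 10.4.3 analyses the amount "with adjustment for baseline value, defined as the average amount over the 6 months prior to the screening visit and clinical site". SAP 9.4 keeps that window ("with adjustment for the measure in the 6 months prior to the screening period and pooled clinical site"), and its sample code for the rank ANCOVA has one baseline variable. SAP 9.2 approximates that variable as the number of infusions times the last amount infused.

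At screening, sites are to "Determine need for parenteral iron therapy based on results of iron studies" (protocol 7.3.1). Baseline follows 28 to 56 days later. The schedule of events records ferritin, iron, TIBC and iron infusions at the baseline visit.

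**The concern.** Two patients with the same on-treatment bleeding can receive different amounts of iron because one starts treatment further below the target. The planned covariate describes infusions before screening, not the state at baseline. It is zero for an anemia-only entrant with no earlier iron, who may need a good deal, and it can be high for someone since repleted. Baseline ferritin and saturation measure that state directly, and the protocol's own infusion guidance makes them prognostic.

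At stake is the sensitivity of one of five key secondary endpoints tested by Hochberg, at thresholds from 0.05 down to 0.010. No other part of the SAP fills the gap. SAP 7.2 limits exploration of imbalanced covariates to the primary outcome, and SAP 7.3 plans no sensitivity analyses for secondary analyses. Iron-replete status and change in ferritin appear in SAP 9.2 only as outcomes.

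**Working it through.** **1. The plan's own figures.** No power is stated for mg of iron. The nearest figure is protocol Table 9, for the proportion with any transfusion or infusion. With 48 placebo and 96 pomalidomide patients and two-sided alpha 0.05, power = Φ[(0.30 − 1.96·SE0)/SE1].

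- 90% v 60%: SE0 = √(0.7·0.3·(1/48+1/96)) = 0.0810; SE1 = √(0.09/48+0.24/96) = 0.0661; power 98.4% (stated 98%).
- 50% v 20%: SE0 = 0.0810; SE1 = √(0.25/48+0.16/96) = 0.0829; power 95.6% (stated 96%).
- With 42:84 patients, 96.7% and 92.9%; with 37:74, 94.3% and 89.6%. All agree with Table 9.

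These figures say nothing about the amount of iron. Its standard deviation, treatment effect and entry deficit are not in the documents, so everything below rests on assumptions.

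**2. What unadjusted entry deficit could cost.** Suppose the comparison would have 90% power without it, and let s be the share of outcome variance it contributes. The standard deviation then grows by 1/√(1−s), and power = Φ[(z(1−α/2) + 1.2816)·√(1−s) − z(1−α/2)]. At alpha 0.05 and s = 0.30: Φ[3.2415·0.8367 − 1.9600] = Φ(0.752) = 77%.

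| s | 10% | 20% | 30% | 40% | 50% |
|---|---|---|---|---|---|
| alpha 0.05 | 87% | 83% | 77% | 71% | 63% |
| alpha 0.01 | 86% | 81% | 74% | 66% | 56% |

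This is the cost of the noise itself. Adjustment recovers only the part that the covariate explains.

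**3. What adjustment could recover.** The SAP's site-stratified rank ANCOVA was simulated with the six pooled sites of SAP 7.6 (51, 24, 21, 21, 16, 12; total 145), 2:1 allocation and 1,500 runs per setting. Assumed: a 35% cut in bleeding-driven iron; 30% of patients with no prior iron; 30% given some run-in iron; baseline iron status correlated 0.7 with the remaining deficit; entry deficit unrelated to prior iron.

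| Mean entry deficit ÷ mean bleeding-driven iron | SAP model | + baseline iron status | + status and run-in iron |
|---|---|---|---|
| 0 | 73.7% | 71.8% | 71.8% |
| 0.25 | 68.5% | 69.7% | 67.2% |
| 0.5 | 58.0% | 59.2% | 57.5% |
| 1.0 | 40.1% | 45.3% | 44.9% |
| 1.5 | 29.0% | 38.9% | 38.6% |

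With no treatment effect, rejection was 4.1% to 6.1% in every variant.

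**4. Other assumed inputs, same test.**

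- A 40% cut in ongoing need, with ferritin tracking the deficit with error: 85.7% to 88.2% (small repletion), 75.0% to 82.5% (moderate) and 52.8% to 71.5% (large). Null rejection was 4.1% to 5.7%.
- Two further sets gave -2 to +3 and -1 to +3 points at small deficits. At large ones they gave +7 to +20 (deficit 50% to 100% of ongoing need) and +4 to +19, the latter depending on how well ferritin tracks the deficit.

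Taken together, the gain is about -2 to +3 points when the deficit is small and about +4 to +20 when it rivals ongoing need. In between, results differ: about +1 at a ratio of 0.5 in the table above, about +7 under other inputs.

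**The case against.** The best defence is that the plan contains no error here. Protocol and SAP agree on the covariate for the iron amount, and adjusting for the same measure over a comparable earlier period, with pooled site, is a valid randomized analysis. This stands. A reader might infer that the comparison is biased, or that a chance imbalance in entry iron would go uncorrected. Neither follows: entry deficit is balanced in expectation, and the nominal error rate already allows for chance imbalance in an unadjusted factor.

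Second, the run-in works against a large carried-in deficit, since iron need is judged at screening and iron may be given before baseline. That is fair, but the documents do not say how much was given, so small and large deficits both remain possible.

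Third, a reader might infer that deficit repletion cannot respond to pomalidomide. That is too strong. Infusion is encouraged, not mandated; iron studies are repeated monthly; and the SAP tracks oral iron. A patient who bleeds less may rebuild stores without an infusion. The simulations treat the deficit as untouched by treatment, which is a simplification.

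Fourth, protocol 4.1 warns that inflammation can raise ferritin. This stands and is a reason to allow saturation as the alternative.

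**Conclusion.** The point holds as a matter of efficiency. A prognostic baseline value, already collected, is left out of the model for a key secondary endpoint, and the one prognostic covariate used is uninformative about the deficit of anemia-only entrants with no earlier iron. The test remains valid.

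The size is not known. The rise from 53% to 71% is a favourable case under assumed inputs and should not be quoted without the rest of the range. At small deficits the change is negligible and may be slightly negative. Even at large ones, adjustment recovers only part of the loss.

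Two further inferences are not supported. Run-in iron lies outside both the covariate and outcome windows, so a reader might expect that extending the prior-iron window to baseline would raise power; in the simulation, run-in iron added nothing once baseline status was in the model. A reader might also count the window mismatch for the no-blood-or-iron outcome as part of this problem. It concerns a different endpoint, outside the Hochberg family, and is a matter of reconciling the two texts.

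**What to change.** In step B of the rank ANCOVA (SAP 9.4), regress the ranked outcome on ranked prior iron and on ranked baseline-visit ferritin or transferrin saturation. Name one of the two in advance and state what is used if the baseline value is missing. Specify this before unblinding; if it comes later, label the analysis supportive and keep the planned model as the test.

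The cost is a sentence in the SAP, one more ranked variable in the code and one more parameter per pooled site. In the site of 12 that leaves 12 − 3 = 9 residual degrees of freedom.

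Optionally, add a supportive comparison of iron given in weeks 12 to 24, after most initial repletion should be over, noting that early leavers contribute nothing to it.

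Separately, reconcile the covariate window for the no-blood-or-iron outcome. SAP 9.4 counts iron and transfusion "in the 6 months before the baseline visit", protocol 10.4.3 counts the 6 months before the screening visit, and SAP section 12 states that nothing changed from the protocol. Choose one window and correct the other text, or list the change in section 12.

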9.5 Exploratory Analysis Methods

Exploratory analyses include estimating the rate of relapse at the 4-week post-treatment follow-up visit, where relapse is defined as a return of the ESS to the baseline value or greater in pomalidomide-treated subjects and estimating the median time after initiation of pomalidomide to obtain a decrease of at least 1.0 in the ESS in pomalidomide-treated compared to placebo subjects. These outcomes will have no statistical testing.

To learn which demographic or biomarkers are predictive of greater response to pomalidomide we will fit generalized linear models to the primary outcome in the pomalidomide treatment group to predict treatment response based on presence of the specific mutations in the endoglin (ENG) or

activin-like kinase (ACVRL1) genes, as well as a set of pre-defined baseline covariates., to include age, gender, and baseline disease severity.

An exploratory analysis will evaluate the correlation of the ESS score and the average daily duration of bleeding from the diary.

An exploratory analysis will also compare groups for total iron taken during the treatment period, combining both oral iron and iron infusions.

9.6 Formal Interim Efficacy Analysis

We will perform a formal interim analysis to evaluate for early overwhelming efficacy based on the change in ESS score from baseline to 24 weeks after 50% and 75% of subjects have completed the 24-week visit or discontinued the study. Futility will also be assessed at 75%, and each formal interim analysis will include a full DSMB safety review.

For assessing early efficacy, the significance level for the interim and final analysis will be based on Lan-DeMets α -spending functions with O'Brien-Fleming boundaries in order to maintain the study-wise α level at 0.05. The α level will be 0.0031 at 50%, 0.0183 at 75% and 0.0440 at the final analysis. The exact α level at the interim will be determined using Lan-DeMets α -spending functions based on the actual percent of data available at the interim.

Assuming 90% power at the end of the study, there is a 26% chance of meeting the stopping boundary at the 50% interim, and a 69% chance at the second interim. If the study actually has 80% power (for example, due to higher-than-expected discontinuation rate or ESS standard deviation), then there is a 54% chance of meeting the stopping boundary at the second interim. Conversely, if the study actually has power $> 95\%$ (for example if treatment group difference in ESS change is 1.2 rather than 1.0 or lower than expected standard deviation), then the chance of stopping is 41% at the first interim and 84% at the second interim.

Futility will be assessed at 75% based on conditional power of the primary efficacy variable. The DSMB may recommend study stop due to futility if the upper limit of the 80% confidence interval for conditional power does not exceed 50%.

With our planned enrollment rate, we expect approximately 6 months of randomization visits to take place after the 50% interim analysis, and so there is a potential to decrease the overall study sample size in the event that the DSMB recommends stopping enrollment based on the interim analysis results. If enrollment proceeds as planned, then randomization will be essentially complete by the time of the 75% interim analysis. In this case, we will request the DSMB to skip the second interim analysis in order to maximize the alpha level at the end of the study. Otherwise, if enrollment is slower than expected, then the results of the second interim analysis still provide a chance to decrease the study sample size.

Both interim analyses were carried out. Details are provided in **Appendix 2** and **Appendix 3**.

